Official Title: Assessing the Safety of Nighttime Passy-Muir Valve Use and its Impact on Sleep Quality in the Long-Term Acute Care Hospital Setting: a Cross-Over Controlled Study

Clinical Trial Number: NCT06229639

Use date of study closeout: 9/1/2016

STUDY PROTOCOL AND STATISTICAL ANALYSIS PLAN

Study Protocol

Eligible participants were inpatients 18 years of age or older, who were admitted to Gaylord Specialty Healthcare following tracheostomy placement during an acute care hospital stay, were eligible for decannulation, and who had a tracheostomy tube size of six or smaller and did not require ventilation assistance. These patients were initially referred to the study by a Respiratory Care Practitioner (RCP). Patients also needed to meet all criteria outlined in Gaylord's decannulation protocol, along with the specific criteria required for the study. (**Table 1**). Eligible patients were then approached for study enrollment. Enrolled participants were given the FDA-approved PMV #2001 for the study. The PMV is a bias-closed, no-leak speaking valve that allows patients to speak at a level consistent with their normal vocalization range.

Participants were monitored and evaluated using the same outcomes and safety metrics typically used during the study site's decannulation protocol. This included an initial and daily evaluation by a Pulmonary or Critical Care Medicine consultant and daily morning arterial blood gas (ABG) measurements by an RCP. The RCP then conveyed ABG measurement to the covering therapists and Pulmonary or Critical Care Medicine consultants at shift change. The RCP then communicated daily with the covering Independent Medical Practitioner (IP). If participants failed to meet the decannulation or study criteria at any point during the protocol, then the IP was notified, and the protocol was to be canceled.

PMV Trial – Study Day One and Night One

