On day one of the study period, participants were given a PMV to use during the day. If the PMV was tolerated without any acute vital changes (i.e., adverse reactions; **Table 2**), participants were instructed to keep the PMV on after 22:00, when it would typically be removed if still in place (**Figure 1**). Throughout the night, participants were kept on continuous telemetry for the duration of the study protocol. Nursing staff monitored and recorded heart rate, blood pressure, and temperature every four hours (e.g., 22:00, 02:00, and 06:00). The Respiratory Therapist (RT) on duty recorded oxygen saturation, end-tidal carbon dioxide (ETCO₂) levels via nasal cannula, and respiratory rate. Supplemental O₂ was given to participants as determined by the clinical opinion of the respiratory staff. Supplemental O₂ was noted if given to participants but not categorized as a serious adverse reaction requiring trial termination.

If at any time the participants experienced serious adverse reactions such as respiratory distress, stridor, or ETCO₂ greater than 60, PMV removal was scheduled (**Table 2**), and initiation of ventilatory support was planned. The trial would then be terminated and deemed unsuccessful. In the event of an unsuccessful PMV trial, the RCP would inform the IP and acquire ABG measurements. If this procedure did not improve the participant's respiratory condition, the next step would be to initiate ventilator support and request a chest X-ray.

Following night one, participants completed the Richards-Campbell Sleep Questionnaire (RCSQ) upon waking. The RCSQ is a six-question self-report questionnaire used to assess ICU patients' sleep quality.¹⁵ These six questions assess the domains of sleep depth, sleep latency, awakenings, ability to return to sleep, overall sleep quality, and overnight noise level.¹⁵ The responses were recorded on a 100 mm visual analog scale, with higher scores indicating better sleep levels than lower scores. The mean score represents the general perception of sleep quality, which was the secondary outcome of this study, evaluated by the sleep domain scores derived from the Richards-Campbell Sleep Questionnaire.

Tracheostomy Plug Trial – Day Two and Night Two

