If study day one and night one were successful, the protocol was continued to day two. During day two, participants wore a tracheostomy cap, also known as a plug. If the plug was tolerated without any adverse response, participants were instructed to keep the tracheostomy plug in place throughout the night. Again, nursing staff monitored and recorded heart rate, blood pressure, and temperature every four hours, and the RT on duty recorded oxygen saturation, ET_{CO}₂ levels, and respiratory rate. Same as night one, if any adverse events or acute changes occurred, it was planned that the plug be removed, ventilator support would be started, and the trial considered a failure. If no adverse events occurred upon waking up following night two, the participants were again administered the RCSQ. Once completed, following night two, participants' roles in the study were done and continued with the decannulation protocol as appropriate.

Statistical Analysis

Continuous clinical and demographic characteristics were described with means and 95% confidence intervals, and categorical data were described with frequencies. Differences in categorical variables were evaluated using Fischer's exact test or Chi-Square testing as appropriate. Differences in continuous variables were analyzed using paired t-tests for normally distributed data and Wilcoxon signed-rank test for non-normally distributed data. Two-way ANOVA analysis and Tukey's multiple comparisons post-hoc test were used to analyze differences in continuous variables at three time points (22:00, 02:00, and 06:00). Complete case analysis was performed on the dataset, with only complete pairs of data from night one and night two at the three time points being included in the analysis. All data were analyzed via GraphPad Prism 9 (GraphPad Software, San Diego, CA). Statistical significance was defined as a p-value less than 0.05.

Criteria for Initiation of Decannulation Protocol and Other Study-Specific Criteria

Decannulation Criteria

Afebrile
Hemodynamically stable
Clear or stable chest x-ray
Controlled Secretions
Peak Cough Flow ≥ 160 L / m
Satisfactory on-going nutrition (low risk of aspiration)
No clinical evidence of tracheal obstruction
Ability to tolerate a speaking valve

Inclusion Criteria

Patient has evidence of respiratory insufficiency requiring a tracheostomy tube without current need for assisted ventilation.
Patient will be continuously monitored with telemetry.

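### Every participant who fails the valve night drops out of the night-one versus night-two comparisons, and the plan names no failure proportion, denominator or interval.

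*Combined protocol and SAP*

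**What the plan says.** The official title puts safety first: "Assessing the Safety of Nighttime Passy-Muir Valve Use and its Impact on Sleep Quality". The PMV Trial section describes sleep quality as the secondary outcome. No section names the primary outcome or how it is to be estimated.

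Four statements fix who can be analysed:

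- **Stopping on night one** (PMV Trial – Study Day One and Night One). The triggers are "serious adverse reactions such as respiratory distress, stridor, or ETCO₂ greater than 60". The consequence is stated as "The trial would then be terminated and deemed unsuccessful".
- **Entry to night two** (Tracheostomy Plug Trial – Day Two and Night Two). "If study day one and night one were successful, the protocol was continued to day two".
- **Sleep questionnaire.** For the PMV night: "Following night one, participants completed the Richards-Campbell Sleep Questionnaire (RCSQ) upon waking". For the plug night it is conditional: "If no adverse events occurred upon waking up following night two, the participants were again administered the RCSQ".
- **Analysis set** (Statistical Analysis). Complete cases, "with only complete pairs of data from night one and night two at the three time points being included in the analysis".

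On summaries, the Statistical Analysis section says: "Continuous clinical and demographic characteristics were described with means and 95% confidence intervals, and categorical data were described with frequencies". Categorical differences are tested with Fisher's exact or chi-square tests. Continuous ones use paired t-tests or signed-rank tests, with a two-way ANOVA over 22:00, 02:00 and 06:00.

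**The concern.** Success on the PMV night is a condition for having any night-two data, and having night-two data is a condition for being analysed. The people in whom the valve had to come off, the most important ones for a safety question, are absent from every comparison of the two nights. Participants who needed only supplemental oxygen can stay in; those whose PMV was removed cannot.

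ETCO₂ has a second problem. It is a measurement to be compared between nights and also a removal trigger, so the paired values are selected on the outcome itself.

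No other part of the plan supplies what the pairs cannot. It names no PMV failure endpoint, no set of all night-exposed participants and no interval for a proportion. A paired result showing similar vital signs on the two nights could then be read as evidence of safety when it describes only people already known to have tolerated the valve. The paired sleep result is limited in the same way.

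**Working it through.** The plan states no sample size, event count or failure rate, so it has no figure to reproduce. The check has three parts.

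**1. Participant flow.** This needs no assumptions.

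- PMV-night failure → participation ends → no plug night → no night-two readings and no second sleep questionnaire → no pair. No repeat PMV night is described. Failures among the paired participants = 0 for any true rate.
- Plug-night adverse event → the second sleep questionnaire is not given → the sleep pair is lost. The vital-sign pair is lost only if readings stop before 06:00, which the text does not settle.

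**2. What a failure proportion would show.** N and failure counts are assumed. Exact (Clopper-Pearson) 95% limits for x failures among n:

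- lower = Beta quantile(0.025; x, n − x + 1)
- upper = Beta quantile(0.975; x + 1, n − x)
- for x = 0, lower = 0 and upper = 1 − 0.025^(1/n)

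| Failures / starters | Proportion | Exact 95% CI | Seen in the paired set |
|---|---|---|---|
| 1/10 | 10% | 0.3% to 44.5% | 0 of at most 9 |
| 2/20 | 10% | 1.2% to 31.7% | 0 of at most 18 |
| 2/30 | 6.7% | 0.8% to 22.1% | 0 of at most 28 |
| 0/10 | 0% | 0 to 30.8% | 0 of at most 10 |
| 0/20 | 0% | 0 to 16.8% | 0 of at most 20 |
| 0/30 | 0% | 0 to 11.6% | 0 of at most 30 |

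The chance of at least one failure is 1 − (1 − p)^n. At n = 20 it is 64%, 88% and 99% for assumed true rates of 5%, 10% and 20%.

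**3. Effect on the paired ETCO₂ difference.** Every input except the threshold of 60 is assumed:

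- participant SD 5.5, participant-by-night SD 3.5, residual SD 3 (mmHg)
- total variance 30.25 + 12.25 + 9 = 51.5, so total SD = 7.2 and between-night correlation = 30.25/51.5 = 0.59
- three readings a night, stopping after the first value above 60; a night-one trigger removes night two; a plug-night trigger at 06:00 keeps all six readings

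Simulation with 400,000 participants per scenario; a separate rerun agreed within simulation error:

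| Plug mean | True PMV − plug rise | Night-one failures | Bias of complete-pairs difference | Share of rise |
|---|---|---|---|---|
| 40 | 0 | 0.6% | −0.01 | – |
| 40 | 5 | 3.6% | −0.17 | 0.17/5 = 3% |
| 40 | 8 | 8.5% | −0.36 | 0.36/8 = 4.5% |
| 45 | 0 | 3.6% | −0.04 | – |
| 45 | 5 | 14% | −0.47 | 0.47/5 = 9% |
| 45 | 8 | 26% | −0.90 | 0.90/8 = 11% |

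The difference is partly protected because selection lowers both nights together. The night-one level alone is distorted more: with a rise of 8, complete pairs put it 1.1 mmHg too low (plug mean 40) or 2.9 mmHg too low (plug mean 45).

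With all available readings and known variance components, generalised least squares with participant and participant-by-night effects had bias of at most 0.01 mmHg in all six scenarios. With a participant intercept only, bias remained: −0.11 and −0.24 (plug mean 40, rises 5 and 8), and −0.32 and −0.58 (plug mean 45, rises 5 and 8).

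**The case against.** The best reply has four parts.

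*The loss is built into the design.* A paired test needs both nights, so a PMV-night failure is missing from it under any missing-data rule. That is true. The complete-pairs sentence does its own harm only in the time-point analysis, and it may have been meant only for that analysis, since it follows the ANOVA sentence. But it is worded as applying to the dataset, and if the loss is inherent in pairing, a separate failure analysis is needed all the more.

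*Failures could be counted as categorical data.* The triggers are given, a failed night is labelled as such, and frequencies are planned for categorical variables. Nothing forbids a tally. This stands, but a permitted tally is not a named endpoint with a denominator and interval. The plan's 95% intervals are stated only for continuous characteristics. The two exhibits not shown (Table 2 and Figure 1) are cited for reactions and procedure, not for analysis.

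*The ETCO₂ bias is small and rests on assumptions.* This stands. The largest value, 0.9 mmHg, needs 26% failures. The simulation also triggers only on three recorded ETCO₂ values, whereas the protocol allows stopping at any time and for respiratory distress or stridor. Adding unrecorded triggers between readings raised the bias of the all-readings analysis to about 0.06 mmHg, still small.

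*The mixed model may not be estimable in a small trial, and the after-22:00 denominator leaves out people stopped on day one.* The model fitted in all 150 simulated trials of 20 participants. The denominator does omit day-one stops, but it suits a question about nighttime use.

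**Conclusion.** The concern holds and must be fixed. By the plan's own flow, no PMV-night failure can enter a night-one versus night-two comparison, and no failure proportion, night-exposed denominator or interval is named for the title's first aim. That conclusion rests on the text alone and does not depend on N or on the true rate.

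Its practical size does depend on unstated figures. If nobody failed the PMV night, no pair is lost for that reason, but the interval is still needed to separate no failures seen from safety shown. If failures occurred, the paired results hide all of them. The distortion of the mean ETCO₂ difference is secondary: 0.0 to 0.9 mmHg under the assumed variances, means and rises. The paired sleep result applies only to participants who completed both nights.

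**What to change.** 1. **Failure proportion (essential).** Make the safety result the proportion failing the PMV night among all participants who kept the valve on after 22:00, with an exact (Clopper-Pearson) 95% CI. Report plug-night failures in the same way over all who started night two.
2. **Repeated readings.** Analyse the 22:00, 02:00 and 06:00 values with a mixed-effects model on all available readings, including those up to termination. Use fixed effects for night, time and night-by-time, and random effects for participant and participant-by-night; a participant intercept alone leaves part of the bias in place. Keep the complete-pairs analysis as a sensitivity analysis.
3. **Sleep.** Report the night-one questionnaire for everyone who completed it beside the paired comparison, and state that the paired result applies only to those who completed both nights.

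The cost is slightly more analysis of data already collected, with no extra patients or measurements. The safety result may look less favourable, and with a small N its interval will be wide.

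### The complete-case rule states no unit of completeness and makes no exception for the sleep questionnaire, so one missed overnight reading can discard usable data

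*Combined protocol and SAP*

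**What the plan says.** The Statistical Analysis section states the rule in one sentence. Its first half names the method: "Complete case analysis was performed on the dataset". Its second half sets the condition for inclusion: "with only complete pairs of data from night one and night two at the three time points being included in the analysis". The preceding sentence assigns two-way ANOVA with Tukey's test to continuous variables at 22:00, 02:00 and 06:00. Other continuous differences are tested by paired t-test or Wilcoxon signed-rank test.

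The data that the rule might cover are described under PMV Trial – Study Day One and Night One, and are collected again on night two:

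- **Nursing readings.** "Nursing staff monitored and recorded heart rate, blood pressure, and temperature every four hours", with the same three clock times given as examples.
- **Respiratory readings.** The Respiratory Therapist "on duty recorded oxygen saturation, end-tidal carbon dioxide" and respiratory rate. No recording times are stated.
- **Sleep.** After night one, "participants completed the Richards-Campbell Sleep Questionnaire (RCSQ) upon waking". It is given again after night two if no adverse event occurred. General sleep quality is the outcome "which was the secondary outcome of this study, evaluated by the sleep domain scores derived from the Richards-Campbell Sleep Questionnaire".

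The document has no separate completeness rule for the RCSQ. It states no sample size, expected missing rate or expected loss.

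**The concern.** This point concerns participants who finish both nights but lack a routine reading. The rule attaches to the dataset as a whole and makes inclusion depend on three clock times. Two difficulties follow.

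- **Sleep outcome.** The RCSQ has no 22:00, 02:00 or 06:00 value, so a condition on those times cannot sensibly decide which questionnaire pairs are analysed. It is nevertheless the only rule given. Taken at its word, it could exclude a participant with two completed questionnaires for a gap in, say, blood pressure.
- **Vital signs.** If completeness is judged per variable across all three times, a missed 02:00 value removes that participant's valid night-one and night-two pairs at 22:00 and 06:00 as well.

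At stake are the precision of the night comparison and the reader's ability to tell who is in the secondary-outcome analysis.

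**Working it through.** The plan has no figure of its own to reproduce.

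**Inputs from the document.** Three clock times × two nights = 6 readings per variable per participant. One night-one/night-two pair at a single clock time = 2 readings.

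**Assumed input.** A missing rate m per reading of 1% to 10%, first taken as independent between readings.

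**Step 1: loss under each reading of the rule.** If k readings are all required, the expected loss is 1 − (1 − m)^k. For example, at m = 5%, six readings give 1 − 0.95^6 = 1 − 0.7351 = 26.5%, and two readings give 1 − 0.95^2 = 9.75%.

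| m | k = 6 (whole variable) | k = 2 (one clock time) | Excess, percentage points |
|---|---|---|---|
| 1% | 5.9% | 2.0% | 3.9 |
| 2% | 11.4% | 4.0% | 7.5 |
| 5% | 26.5% | 9.8% | 16.7 |
| 10% | 46.9% | 19.0% | 27.9 |

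Solving for m, a loss of 25% needs m = 1 − 0.75^(1/6) = 4.7%, and a loss of 50% needs m = 1 − 0.5^(1/6) = 10.9%.

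**Step 2: clustered gaps.** Missed readings may fall in the same participants. Under a beta-binomial model with intraclass correlation ρ, let s = 1/ρ − 1, a = ms and b = (1 − m)s. The loss is then 1 − B(a, b + 6)/B(a, b).

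| m | Independent | ρ = 0.1 | ρ = 0.5 |
|---|---|---|---|
| 5% | 26.5% | 21.7% | 11.7% |
| 10% | 46.9% | 39.4% | 22.3% |

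**Step 3: precision.** The simulation assumes 20 participants and SDs of 1.5 (participant), 0.7 (participant-by-night) and 1.0 (single reading). It compares the variance of the estimated night difference with that from an analysis of all recorded readings.

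| m | Six-reading deletion |
|---|---|
| 1% | about 6% higher |
| 2% | about 13% higher |
| 5% | about 36% higher |
| 10% | about 86% higher |

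Under per-clock-time deletion the increase is only about 1% to 7% over the same range. A rough check needs no SDs: variance scales with 1/(1 − loss), which gives 1/0.9415 = 1.06, 1/0.8858 = 1.13, 1/0.7351 = 1.36 and 1/0.5314 = 1.88. Other estimators of the all-readings analysis gave 33% to 38% at m = 5% and 77% to 86% at m = 10%.

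**Step 4: which reading touches the RCSQ.** Six is the count for one variable, and under that reading the RCSQ is unaffected. The RCSQ is affected only if completeness is judged across the participant's whole record. With six variables that is 36 readings, and independent loss would be 30%, 52%, 84% or 98% at m = 1%, 2%, 5% or 10%. That count also assumes that the respiratory readings share the three clock times, which the document does not say, and clustering would cut it sharply (53% to 19% at m = 5% for ρ from 0.1 to 0.5). The conclusion therefore does not rest on the 36-reading figures.

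**The case against.** The strongest reply is that the rule was never meant for the RCSQ. It follows directly after the ANOVA sentence and repeats its reference to three time points, and the word pairs suits matched values better than removal of whole participants. On that reading the sleep comparison is untouched. This is plausible, so exclusion from the RCSQ analysis is a possible consequence of ambiguous text and not something the plan states. The need for clarification remains, because the plan would then have no completeness rule for its secondary outcome.

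Second, some deletion is inherent in the methods chosen. A paired comparison at one clock time needs both nights, and a balanced repeated-measures ANOVA needs complete cells. The first part stands. The second is uncertain, because the plan does not say that its two-way ANOVA is repeated-measures.

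Third, if pairs are dropped per clock time, the precision cost is small and the choice of a mixed model is largely a preference. That also stands: the practical gain depends on which reading was applied.

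A reader might go further and infer that good sleepers are selectively lost, because a 02:00 check is easily skipped in someone asleep. The documents contain nothing to support this. Even in a scenario constructed that way, with 02:00 skipped in 20% of good and 5% of poor sleepers, the device difference barely moved (9.98 v 9.94 mm).

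**Conclusion.** The concern holds in a limited form. The rule is written for the dataset, is tied to three clock times, states no unit of completeness and has no RCSQ exception. Depending on the reading, it either could remove valid questionnaire pairs or can discard five valid readings of a variable for one gap.

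The size is conditional. Six-reading deletion loses about 6% to 47% of participants for a variable at an assumed independent missing rate of 1% to 10%, and less if gaps cluster. The variance increase of about 6% to 86% also depends on the assumed 20 participants and SDs, and it falls to about 1% to 7% if deletion is per clock time.

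A reader might infer that the design loses a quarter to a half of its pairs. The documents do not support that as a general statement, because it needs roughly 5% to 11% of readings missing independently and no rate is given. Nor can the six-reading loss be carried over to the sleep outcome, since the reading that requires six values leaves the RCSQ alone.

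**What to change.** Replace the single sentence with two rules and a reporting requirement.

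1. **RCSQ.** Include every participant with both questionnaires, whatever vital-sign readings are missing.
2. **Vital signs.** For each variable, fit a linear mixed model to all recorded readings, with night, time and night-by-time as fixed effects and participant and participant-by-night as random effects. Keep the complete-pairs result as a sensitivity analysis, and state the unit at which completeness is judged there.
3. **Reporting.** Give the number analysed for each outcome.

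The cost is revised SAP wording and a re-run, with no new data. There are two small drawbacks: the number analysed will differ between outcomes, and the mixed model assumes that readings are missing at random.

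### Safety is the study question, but the SAP infers only from difference tests at p<0.05 and plans no interval for the valve-night failure rate or the paired night difference

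*Combined protocol and SAP*

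**What the plan says.** The official title opens with "Assessing the Safety of Nighttime Passy-Muir Valve Use". The section on study day one and night one names sleep quality as the secondary outcome.

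The Statistical Analysis section sets these rules:
- Description: "Continuous clinical and demographic characteristics were described with means and 95% confidence intervals, and categorical data were described with frequencies".
- Categorical outcomes: "Differences in categorical variables were evaluated using Fischer's exact test or Chi-Square testing as appropriate".
- Continuous outcomes: "Differences in continuous variables were analyzed using paired t-tests for normally distributed data and Wilcoxon signed-rank test for non-normally distributed data", plus a two-way ANOVA with Tukey comparisons over the three overnight time points.
- Decision rule: "Statistical significance was defined as a p-value less than 0.05".
- Analysis set: complete cases, meaning participants with paired data from both nights at the three time points.

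Failure is defined for the individual. After a serious adverse reaction on the valve night, "The trial would then be terminated and deemed unsuccessful". The order of nights is fixed and conditional: "If study day one and night one were successful, the protocol was continued to day two".

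The text supplied gives no sample size, power, margin or acceptable failure rate.

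**The concern.** The result that favours the valve is a null result: no significant difference between nights and few or no failures. A difference test is built to detect a difference. When it does not, the data may show that the nights are alike, or there may simply be too few patients to tell. An interval separates the two cases, and the plan has none for the two quantities that carry the safety question.

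The sequence and the analysis set add a second problem. A participant who fails on the valve does not go on to the plug night and so has no pair. The outcome of most interest is therefore removed from the comparison before any test is run.

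At stake is whether a reader of the results can tell a low failure rate from an imprecisely measured one.

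**Working it through.** The plan gives no figure to reproduce, because no N, event rate or margin is stated. N below is an assumption, shown over a range. Tests are taken as two-sided, since the plan does not say.

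**Step 1. What the analysis set can contain.** Inclusion needs data from both nights. Night two needs a successful night one. So everyone in the analysis set passed the valve night, and the valve-failure count there is 0 whatever the true rate. For example, if 5 of 20 starters fail (5/20 = 25%), the complete pairs show 0/15.

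**Step 2. What zero failures excludes.** The exact two-sided 95% upper bound for 0/n is 1 − 0.025^(1/n).

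| n starting the valve night | Upper bound |
|---|---|
| 10 | 1 − 0.025^(1/10) = 0.308 |
| 20 | 1 − 0.025^(1/20) = 0.168 |
| 30 | 1 − 0.025^(1/30) = 0.116 |
| 50 | 0.071 |
| 100 | 0.036 |

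The denominator matters. In the Step 1 example, an exact interval computed on the completers has upper bound 1 − 0.025^(1/15) = 0.218. That is below the 25% actually seen among starters, so adding an interval to the complete pairs would not repair the problem.

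**Step 3. What a difference test would do if failures were tested.** Suppose the pair restriction is not applied to failures, 5 of n fail on the valve, and none of the n − 5 who reach the plug night fail. The total is 2n − 5 with 5 failures. The Fisher probability of this table is C(n,5)/C(2n−5,5), and the two-sided p adds every table that is no more probable.

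- n=10, 5/10 vs 0/5: observed 252/3003. The other tail has 1 or 0 failures on the valve: (50 + 1)/3003. p = 303/3003 = 0.10.
- n=20, 5/20 vs 0/15: observed 15504/324632, other tail 3003/324632. p = 18507/324632 = 0.057.
- n=30, 5/30 vs 0/25: observed 142506/3478761, other tail 53130/3478761. p = 195636/3478761 = 0.056.

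Failure rates of 50%, 25% and 17% on the valve against none on the plug are all non-significant. By the same method 5/50 vs 0/45 gives 0.058 and 5/100 vs 0/95 gives 0.060, so the undetected rate falls to 10% and 5% as N grows. Fisher's test is used because the plan names it; it treats the nights as independent samples, although the same people contribute to both.

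**Step 4. Continuous safety measures.** The paired t-test and Wilcoxon test deliver p-values. A CI for each night's mean, if one is reported, is not a CI for the within-patient difference. The documents give no SD for paired differences, so no width is calculated here.

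**The case against.** **The plan never says that a non-significant result means safe.** That is correct. A reader might infer such a rule because p<0.05 is the only threshold given, but the text does not state how a null result would be read. The point is that the plan offers no inference that would make a null result informative.

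**Safety criteria do exist.** This also stands. The valve-night section lists reactions that make an individual's trial unsuccessful, and frequencies are planned for categorical data, so failures can be counted and reported. Table 2, cited for adverse reactions, is not in the supplied text and is not held against the plan. It would be wrong to say the study has no safety criterion. What is missing is any expression of uncertainty about the failure rate at study level.

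**Failure is not named as a tested variable.** True, so Step 3 is conditional. A reader might picture a Fisher test with equal numbers on both nights, such as 4/10 vs 0/10. The design cannot produce that table, because those who fail on the valve do not reach the plug night. If failure is not tested at all, it receives a bare frequency, and the gap is the same.

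**The planned CIs may cover clinical measures.** Possibly, since clinical characteristics could include ETCO2 and vital signs. Those would still be intervals for means, not for the paired difference.

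**An interval without an acceptable limit gives no safe/unsafe verdict.** True. An interval shows which failure rates the data exclude and leaves the judgement to the reader, which is as far as this plan can go without a limit set in advance.

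**The study is closed.** The document is in the past tense with a 2016 closeout. The change needs only data already collected.

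**Conclusion.** The concern holds in a limited form. Following the plan exactly cannot support a safety conclusion from a null result, because its inference consists of difference tests and it plans no interval for the valve-night failure proportion or the paired night difference. Conditional progression to night two, combined with complete-pair analysis, takes valve failures out of the comparison if the text is read literally.

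The size depends on an unstated N. Zero failures would leave an upper bound of 31%, 17% or 12% at 10, 20 or 30 starters, and about 4% at 100. The Fisher illustrations assume that failure is tested, that no plug failures occur and that tests are two-sided. The documents do not support a claim that the study treats non-significance as proof of safety, or that a large excess was in fact hidden.

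**What to change.** Amend the analysis plan, or the reporting now that the study is closed, as follows:

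1. Report the proportion of valve-night failures among all who started the valve night, outside the complete-pair restriction, with an exact 95% CI. Word the conclusion as the failure rate that the data exclude.
2. For each vital sign and ETCO2, report the paired night difference with its 95% CI, and state that it applies only to participants who completed both nights.
3. State that p>=0.05 will not be read as evidence of safety.

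The cost is a few sentences and a few extra output lines, with no new data and no change to any clinical rule. The downside is that the safety statement will look less favourable if the sample is small.
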